8.2.2 Secondary Efficacy Endpoints

8.2.2.1 The changes from baseline at Weeks 5, 9 and 15 in the SIB total score

The change from baseline at Week 5, 9 and 15 in the SIB total score will be summarized descriptively and compared using ANCOVA adjusted for baseline SIB total score.

If the normality assumption is not met, a non-parametric method or a rank-ANCOVA analysis will be used.

8.2.2.2 The changes from baseline at Weeks 5, 9, 13 and 15 in the SIB total score for subjects in the MMSE-2 4-9 stratification group

The change from baseline at Week 5, 9, 13 and 15 in the SIB total score for subjects in the MMSE-2 4-9 stratification group will be summarized descriptively. Similar analysis methods as the primary endpoint will be used for analysis of this endpoint.

8.2.2.3 The changes from baseline at Weeks 5, 9, 13 and 15 in the SIB total score for subjects in the MMSE-2 10-15 stratification group

The change from baseline at Week 5, 9, 13 and 15 in the SIB total score for subjects in the MMSE-2 10-15 stratification group will be summarized descriptively. Similar analysis methods as the primary endpoint will be used for analysis of this endpoint.

8.2.2.4 Individual patient's slope over time in SIB total score evaluated via Weeks 0, 5, 9 and 13

Individual-specific SIB slopes will be estimated for all patients over each person's available SIB outcome measures. An indicator will be assigned to each patient depending on the sign of the SIB slope β (i.e. $I=-1$ if $\beta < 0$; 1 if $\beta > 0$; no value otherwise). The proportions of patients with $I=1$ and, respectively, -1 will be compared using logistic regression to assess the overall trend between treatments. In addition, an overall population averaged slope will be estimated for each treatment arm, and two-sample t-test will be used to assess the difference between treatments.

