3. SAMPLE SIZE DETERMINATION AND RATIONALE, STATISTICAL POWER, AND SIGNIFICANCE LEVEL

Based on post hoc analyses of the NTRP 101-202 study for patients not treated with memantine, the SIB for the 20ug bryostatin group demonstrated a mean (SD) increase of 4.5 (6.8) points from baseline by Week 13. In contrast, patients not treated with memantine in the placebo arm showed a decrease in SIB scores at the 13-week time-point from baseline, giving a mean (SD) SIB change of -0.9 (6.7) points. This resulted in group difference in means of the 13-week SIB measure from baseline SIB changes of 5.4 points.

Guided by these post hoc results, power analyses were performed based on 50 patients per treatment arm, and assuming differences of between 4.0 to 5.5 points in the treatment arm-specific means of the primary outcome (e.g. the treatment effect). Table 3-1 below gives the estimated power to detect various treatment effects, assuming a two-sided alpha of 0.05. Based on these analyses, 50 patients per group will give an approximate 83% power to detect a treatment effect of 4.0 points, and an estimated power of 98% to see a treatment effect of 5.5 points. Power calculation was based the two-sample t-test of the group difference in the mean 13-week SIB changes from baseline SIB.

Table 3-1: Power to detect treatment effect sizes of between 4.0 to 5.5 points; 50 patients per group with an available primary efficacy endpoint.

Diff. in Deltas	Power	N1	N2	Two-sided Alpha
4	83%	50	50	0.05
4.5	91%	50	50	0.05

5	95%	50	50	0.05
5.5	98%	50	50	0.05

Power analyses were also performed to determine detectable effect sizes that assume an estimated dropout rate of 25% (e.g. 50 patients per group at a baseline, dropping to 37 patients per group by Week 13). Table 3-2 gives the estimated powers for treatment effects of between 4.5 and 5.5 points, assuming a 25% dropout rate. Note that a minimum treatment effect of 4.5 points can be statistically detected with at least 80% power, given 37 patients per group with a primary efficacy endpoint.

Table 3-2: Power to detect treatment effect sizes of between 4.5 to 5.5 points; 37 patients per group with an available primary efficacy endpoint.

Diff. in Deltas	Power	N1	N2	Two-sided Alpha
4.5	80%	37	37	0.05
5	88%	37	37	0.05
5.5	93%	37	37	0.05

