7.7 Stratification Factors and Subgroups

This is a randomized study and stratified so that the groups have similar distribution of MMSE-2 score (4-9 vs. 10-15). The stratification will ensure balance between each treatment group in each stratum.

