8.2 Analysis of Efficacy Data

The primary analysis will be conducted on FAS population. The CAS population will be used as a supportive analysis. All statistical tests for efficacy will be two-sided tests, with $\alpha=0.05$.

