8.2.1 Primary Efficacy Endpoint

The primary endpoint for this study is the change from baseline to Week 13 in the SIB total score.

The change from baseline to Week 13 in the SIB total score will be summarized descriptively and compared using Analysis of Covariance (ANCOVA) adjusted for baseline SIB total score.

If the normality assumption is not met, a non-parametric method or a rank-ANCOVA analysis (i.e., an ANCOVA analysis on rank-transformed data) will be used.

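### The SIB slope test omits baseline SIB, which the SAP's whole-population SIB change analyses adjust for: a valid test, but with some precision given up at no saving

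*SAP*

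**What the plan says.** SAP 8.2.2.4 and protocol 9.5.4 describe the slope endpoint in the same way. A slope is fitted to each patient's available SIB scores over Weeks 0, 5, 9 and 13. Slope signs are compared by logistic regression, with no covariate named. For mean slopes, a "two-sample t-test will be used to assess the difference between treatments".

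The neighbouring analyses differ. In SAP 8.2.1 the Week 13 change is "compared using Analysis of Covariance (ANCOVA) adjusted for baseline SIB total score", and SAP 8.2.2.1 applies the same model to Weeks 5, 9 and 15. Neither model names MMSE-2 stratum, although SAP 7.7 says the trial is "stratified so that the groups have similar distribution of MMSE-2 score (4-9 vs. 10-15"). SAP 7.6 allows stratification factors and baseline values as covariates for primary, secondary and additional endpoints, but does not require them. SAP 7.3.1 fixes stratum only in the imputation model.

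**The concern.** Week 0 SIB is one of the four points in each slope and carries the largest weight. A score that is low by chance at Week 0 therefore makes that patient's slope steeper. Conditioning on baseline SIB removes this component; a t-test cannot. The optional clause in SAP 7.6 does not settle the matter, because the named method has no covariates and the clause does not say which would be used.

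Two things are at stake. The slope comparison is less precise than the collected data allow. It may also differ from the ANCOVA results partly because of baseline imbalance rather than treatment.

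**Working it through.** **Inputs from the documents.** Two-sided alpha is 0.05 (SAP 8.2). SAP section 3 gives a "mean (SD) increase of 4.5 (6.8) points from baseline by Week 13" on bryostatin and, for placebo, "giving a mean (SD) SIB change of -0.9 (6.7) points". Sample sizes are 50 per arm, or 37 after 25% dropout. Baseline SIB SD, slope SD and the baseline-slope correlation are not given.

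**Reproducing the plan's power.** Pooled SD = sqrt((6.8² + 6.7²)/2) = 6.75. The plan states "50 patients per group will give an approximate 83% power to detect a treatment effect of 4.0 points". The noncentral t gives 83.5%. The other rows reproduce as 91.0, 95.6 and 98.1% at 50 per arm (stated 91, 95, 98) and 80.8, 88.2 and 93.3% at 37 per arm (stated 80, 88, 93). These figures concern Week 13 change, not slope: "Power calculation was based the two-sample t-test of the group difference in the mean 13-week SIB changes from baseline SIB". No power is stated for the slope.

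**Slope weights.** The times 0, 5, 9, 13 have mean 6.75 and Sxx = 92.75. Weight = (t − 6.75)/92.75, giving −0.0728, −0.0189, +0.0243 and +0.0674. Week 0 has 40% of the total absolute weight. The weights change if visits are missing; with Weeks 0, 5 and 9 only, the Week 0 weight is −0.1148.

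**Assumed model.** All variance in change is independent visit error with SD e, and all four visits are present.

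- 2e² = 6.75², so e = 4.77 and e² = 22.78.
- Slope SD over 13 weeks = 13 × 4.77/sqrt(92.75) = 6.44.
- Unadjusted power for 4.0 points at SD 6.44: 75.0% at 37 per arm, 86.7% at 50 per arm.
- Slope SD per week = 6.44/13 = 0.4956. Correlation with baseline = −0.0728 × 22.78/(0.4956 × SD_B) = −3.35/SD_B, where SD_B is the assumed baseline SIB SD.
- Adjusted power uses residual SD = 6.44 × sqrt(1 − R²), with R² the squared correlation and one degree of freedom fewer.

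| Assumed SD_B | Correlation | R² | Power, 37 per arm (gain) | Power, 50 per arm (gain) |
|---|---|---|---|---|
| 8 | −0.42 | 17.5% | 82.6% (+7.6) | 92.3% (+5.5) |
| 10 | −0.33 | 11.2% | 79.8% (+4.8) | 90.3% (+3.6) |
| 12 | −0.28 | 7.8% | 78.3% (+3.3) | 89.3% (+2.5) |
| 16 | −0.21 | 4.4% | 76.8% (+1.8) | 88.2% (+1.4) |
| 20 | −0.17 | 2.8% | 76.2% (+1.2) | 87.6% (+0.9) |
| 25 | −0.13 | 1.8% | 75.7% (+0.7) | 87.3% (+0.6) |

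Gains are smaller if true slopes vary between patients.

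**Baseline imbalance.** At 50 per arm, one standard error of the baseline difference is SD_B × sqrt(2/50) = 0.2 SD_B. The expected shift in the 13-week slope contrast has size 13 × 0.0728 × 22.78 × 0.2/SD_B = 4.31/SD_B. That is 0.54 points at SD_B = 8 and 0.17 points at 25, against a 4.0-point effect.

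**Stratum.** A simulation used 6,000 runs per scenario, 50 per arm, equal strata whose baseline means differ by 1.2 SD (assumed), and SD_B of 12 and 20. With no slope difference between strata, the t-test's type I error was 5.0 to 5.1%. With strata assumed to differ by 4 points over 13 weeks it was 4.0 to 4.2%. In that second case power at 4.0 points was:

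| SD_B | t-test | Baseline SIB only | Baseline SIB and stratum |
|---|---|---|---|
| 12 | 84.8% | 85.1% | 90.0% |
| 20 | 85.0% | 85.0% | 88.4% |

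In this setting baseline SIB alone adds almost nothing and both covariates are needed.

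**The case against.** The strongest reply is that nothing is invalid. Randomisation makes the unadjusted contrast unbiased, type I error is at or below 5%, and the endpoint is secondary. That stands, so this is a matter of efficiency.

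A reader might infer that the slope also stands apart from the other SIB endpoints in ignoring the randomisation stratum. It does not: the ANCOVAs in SAP 8.2.1 and 8.2.2.1 name baseline SIB only. The inconsistency concerns baseline SIB alone.

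A reader might also infer that a baseline imbalance passes into the slope wholly uncorrected, and only there. Neither follows. A slope through Week 0 already contrasts later scores with baseline, so only the regression-to-the-mean part remains. Nor is every other SIB test securely adjusted: protocol 3.1 bases the primary hypothesis test on a two-sample t-test, protocol 9.4 names no adjusted test, and the SAP's fallback for non-normal data permits an unspecified non-parametric method.

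Large power gains are likewise unsupported. At 37 per arm, 5 points requires a baseline SIB SD of about 10 or less. That looks narrow for a 0-100 scale with entry at MMSE-2 4-15 and SIB up to 93, although the documents do not give the SD.

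SAP 7.6 is a partial answer. The logistic regression could take covariates under it, but the t-test could not, and optional wording does not fix the choice before unblinding.

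**Conclusion.** The point holds as a modest gain in precision. The slope comparison is valid, and conservative if stratum predicts slope. It omits a baseline value that the SAP's whole-population change analyses use. Under the all-visit-error model, the gain from baseline SIB is about 0.6 to 2 points of power at an assumed baseline SD of 16 to 25, and about 6 to 8 points at an SD of 8. Baseline SD, error structure and complete visits are all assumptions, as is the stratum difference in slope used in the simulation. The primary analysis and sample size are unchanged. Free improvement.

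**What to change.** In SAP 8.2.2.4 and protocol 9.5.4, replace the t-test with a linear model of individual slope on treatment, baseline SIB and MMSE-2 stratum. Report the adjusted slope difference with its 95% CI. Name the same two covariates in the logistic regression on slope sign.

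The cost is one sentence in the SAP, the matching line in the protocol, and 2 degrees of freedom. No new data are needed, and the covariates are then fixed before unblinding.

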8.2.3 Exploratory Endpoints

The exploratory endpoints will be analyzed as follows:

8.2.3.1 Change from baseline in ADCS-ADL-Sev total score

The change from baseline in ADCS-ADL-Sev total score will be calculated for each subject using the formula in Section 7.8.4. Similar analysis methods as the primary endpoint will be used for analysis of this endpoint.

8.2.3.2 Change from baseline in MMSE-2 total score

The change from baseline in MMSE-2 total score will be calculated for each subject using the formula in Section 7.8.4. Similar analysis methods as the primary endpoint will be used for analysis of this endpoint.

8.2.3.3 Change from baseline in NPI total score

The change from baseline in NPI total score will be calculated for each subject using the formula in Section 7.8.4. Similar analysis methods as the primary endpoint will be used for analysis of this endpoint.

8.2.3.4 CGI-I score

CGI-I score will be summarized descriptively. Similar analysis methods as the primary endpoint will be used for analysis of this endpoint.

8.3 Analysis of Safety Data

For continuous variables, data will be summarized by treatment using n, mean, SD, minimum and maximum values. For categorical variables, data will be summarized by treatment using frequency and percentage.

8.3.1 Adverse Events

Adverse events will be coded using the most recent version of Medical Dictionary for Regulatory Activities (MedDRA). Treatment Emergent AE's (TEAE) are defined as events with an onset on or after the first randomized treatment. TEAEs will be summarized by treatment group, System Organ Class, and preferred term. The following TEAE summaries will be provided:

- Overall (*i.e.*, regardless of severity or relationship to treatment)
- By severity grade (mild, moderate, severe, life threatening or death for SAEs)
 - By relationship to clinical trial treatment (definitely related, probably related, possibly related, unlikely related, unrelated)

Unless otherwise specified, at each level of subject summarization, a subject will be counted only once. If there is more than one occurrence of an event, the event of the worst severity or the worst-case relationship category will be summarized.

In addition, separate summaries of serious adverse events, and adverse events resulting in discontinuation of study treatment will be presented.

AEs leading to premature discontinuation of clinical trial treatment, AEs that lead to study discontinuation, AEs that lead to death and Serious Adverse Events (SAEs) will also be summarized by treatment group and relationship.

8.3.2 Clinical Laboratory Evaluations

All available results of the clinical laboratory evaluations will be listed and summarized as follows:

8.3.2.1 Laboratory Values over Time

Summary statistics of raw data and change from baseline values for each laboratory parameter will be presented by treatment group and time point. Data will be summarized as appropriate for the variable type.

- For continuous data, summaries will include the number of observations, mean, SD, median, minimum, and maximum values.
- For categorical data, frequency counts and percentages will be used.

For change from baseline summaries, subjects with an undefined change from baseline, because of missing data, will be excluded.

8.3.2.2 Individual Subject Changes (Shift Tables)

Individual subject changes will be identified through shift tables. Shift tables will be presented for each laboratory parameter with counts and percentages of subjects, by treatment group and time point, for shift (change) from baseline, using the normal ranges from the laboratory.

8.3.2.3 Individual Clinically Significant Abnormalities

Clinically significant laboratory abnormalities (i.e., those laboratory abnormalities recorded as AEs) will be listed.

All results of laboratory evaluations will be presented as by-subject listings.

8.3.3 Physical Examination

All physical examination findings will be listed and/or summarized by treatment group. Shift tables will also be presented to show any abnormality shifts from baseline to post baseline visits.

8.3.4 Vital Signs

Tabulations of raw data and change from baseline values will be presented by time point for each vital sign parameter.

Tabulations will include the number of observations, mean, standard deviation, median, and minimum and maximum values. For change from baseline summaries, subjects with an undefined change from baseline, because of missing data, will be excluded.

8.3.5 ECG

All ECG findings will be listed and/or summarized. Shift tables will also be presented to show any abnormality shifts from baseline to post baseline visits.

8.3.6 Columbia Suicide Severity Rating Scale (C-SSRS)

All data from C-SSRS will be listed. Descriptive summaries will be presented for each of the

subscales (i.e. Suicidal Ideation and Suicidal Behavior).

9. APPENDIX 1: SCHEDULE OF ASSESSMENTS

		NTRP101-203										
Week	Screening	0	1	2	3	5	7	9	11	13	15/ET	
Day (±2 days)	(Days -28 to -2) ^d	0	7	14	21	35	49	63	77	91	105	
Dose	Rand	1	2		3	4	5	6	7			
Informed Consent	X											
Medical history	X											
Demographics	X											
Rosen-modified Hachinski Scale	X											
SIB	X [^]					X*		X*		X	X	
MMSE-2	X					X*		X*		X	X	
ADCS-ADL-Sev ^b	X					X*		X*		X	X	
NPI ^b	X					X*		X*		X		
CGI-I						X*		X*		X		
CSSRS	X			X			X*			X		
Labs ^{^^}	X			X			X*			X		
ECG	X (x3)			X			X			X		
PE	X						X ⁺			X		
Vitals	X	X ^c	X ^c	X	X ^c	X ^c	X ^c	X ^c	X ^c	X ^c	X	X
Randomization		X ^a										
Confirm Eligibility	X ^o	X										
Study Drug Dosing		X	X		X	X	X	X	X	X		
Adverse Events	X	X	X	X	X	X	X	X	X	X	X	
Con meds	X	X	X	X	X	X	X	X	X	X	X	

[^]Baseline SIB administered during screening must be done within 3 weeks of the first dose of study drug. If the screening period exceeds 3 weeks, the SIB should be repeated on the day of first dose, prior to dosing; * before dose; ^^Labs: CBC including differential, coagulation, clinical chemistry, TSH at screening (B12, T-3 and T-4 if TSH abnormal), CPK at screening and event of myalgia, βhCG if indicated, HbA1C if clinically indicated; ^o CT scan if necessary per inclusion criterion #6; ⁺ abbreviated physical examination; ^a Randomization after initial screening procedures indicate eligibility; ^b The ADCS-ADL-Sev and NPI may be administered via telephone at the discretion of the investigator, within the allowed time window for the scheduled visit; ^c Vital signs prior to infusion, then at 30, 60 and 90 minutes from start of the infusion (+/- 5min). ^dThe visit window of ±2 Days does not apply to the Screening and Randomization period which is a maximum of 28 days.

10. APPENDIX 2 – PLANNED TLG

10.1 Planned by-subject listings

DISPOSITION/WITHDRAWALS (LISTINGS 16.2.1.X)

ELIGIBILITY (LISTINGS 16.2.2.X)

EXCLUDED SUBJECTS (LISTINGS 16.2.3.X)

DEMOGRAPHICS, POPULATION, AND BASELINE CHARACTERISTICS
(LISTINGS 16.2.4.X)

DRUG COMPLIANCE AND DRUG CONCENTRATION LISTINGS (LISTINGS
16.2.5.X)

EFFICACY RESPONSE (LISTINGS 16.2.6.X)

ADVERSE EVENT DATA (LISTINGS 16.2.7.X)

SAFETY DATA (LISTINGS 16.2.8.1.X)

10.2 Planned Summary Tables

POPULATION DISPOSITION

POPULATION DEMOGRAPHICS AND BASELINE CHARACTERISTICS

CONCOMITANT MEDICATION USAGE

EFFICACY SUMMARIES

SAFETY SUMMARIES

ADVERSE EVENT SUMMARIES

SERIOUS ADVERSE EVENTS

LABORATORY

VITAL SIGNS AND PE

OTHER SAFETY

11. VERSION HISTORY

This is the first version of this document.

